## 8.4 UNANTICIPATED PROBLEMS

---

### 8.4.1 DEFINITION OF UNANTICIPATED PROBLEMS (UP)

An unanticipated problem will be defined as any incident, experience, or outcome that meets ALL of the following criteria:

- Unexpected (in terms of nature, severity, or frequency) given (a) the research procedures that are described in the protocol-related documents, such as the REB-approved research protocol and informed consent document, or the Investigator Brochure; and (b) the characteristics of the research participant population being studied; and
- Related or possibly related to participation in the research (possibly related means there is a reasonable possibility that the incident, experience, or outcome may have been caused by the [investigational product(s)] or procedures involved in the research); and
- Suggests that the research places research participants or others at a greater risk of harm (including physical, psychological, economic, ethical or social harm) than was previously known or recognized.

---

### 8.4.2 UNANTICIPATED PROBLEM REPORTING

The investigator will report unanticipated problems (UPs) to the reviewing Institutional Review Board (IRB). The UP report will include the following information:

- Protocol identifying information: protocol title and number, PI's name, and the IRB project number;
- A detailed description of the event, incident, experience, or outcome;
- An explanation of the basis for determining that the event, incident, experience, or outcome represents an UP;
- A description of any changes to the protocol or other corrective actions that have been taken or are proposed in response to the UP.

To satisfy the requirement for prompt reporting, UPs will be reported using the following timeline:

- UPs that are serious adverse events will be reported to the IRB within 2 days of the investigator becoming aware of the event.
- Any other UP will be reported to the IRB within 7 days of the investigator becoming aware of the problem.
- All UPs should be reported to appropriate institutional officials (as required by an institution's written reporting procedures) within 7 days of the IRB's receipt of the report of the problem from the investigator.

### 8.4.3 REPORTING UNANTICIPATED PROBLEMS TO PARTICIPANTS

Participants will be made aware of any unanticipated problems that have occurred that may indicate that the risk/benefit ratio of study participation has changed.

## 9 STATISTICAL CONSIDERATIONS

### 9.1 STATISTICAL HYPOTHESES

- Primary Efficacy Endpoint(s):
  1. Pulse Wave Velocity will be increased following exercise, smoking high THC cannabis, and vaporizing high THC cannabis relative to resting baseline; effects of cannabis consumption and exercise are likely to be additive. Vaporizing high CBD cannabis will not increase pulse wave velocity.
  2. Percent flow mediated dilation will be decreased following exercise and smoking high THC cannabis; effects are likely to be additive. Vaporizing both high THC and high CBD cannabis will not decrease percent flow mediated dilation.
  3. Ejection fraction will be decreased following smoking and vaporizing high THC cannabis. Exercise and vaporization of high CBD cannabis will not be associated with reductions in ejection fraction.
  4. E/A Ratio will be decreased following high THC cannabis smoking only.
  5. Myocardial strain will be decreased following high THC cannabis smoking and vaporizing only.
  6. Myocardial twist will be decreased following high THC cannabis smoking and vaporizing only.
  7. Burst Frequency will be increased following high THC cannabis only.
  8. Burst Incidence will be increased following high THC cannabis only.

- Secondary Efficacy Endpoint(s):
  1. Systolic Blood Pressure will be increased following cannabis consumption and will be decreased following all bouts of exercise.
  2. Diastolic blood pressure will be unchanged under all conditions
  3. Heart rate will be increased following cannabis consumption and exercise.
  4. Stroke volume will be increased with exercise, and will be reduced following cannabis consumptions. These competing effects will result in an attenuation of increases in stroke volume when exercise is preceded by cannabis consumption.
  5. Cardiac output will be unchanged under all conditions
  6. Work completed will be reduced when preceded by cannabis consumption of all forms
  7. Average power output will be reduced when preceded by cannabis consumption of all forms
  8. Oxygen consumption will be reduced when exercise is preceded by consumption of high THC cannabis
  9. Rating of Perceived Exertion will be increased following consumption of high THC cannabis
  10. Rate-pressure product will be increased during exercise, when the bout is preceded by cannabis consumption.

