### 1.3 SCHEDULE OF ACTIVITIES (SOA)

Procedure	Introductory Visit (Visit 0), Day 0	Exercise Control Visit (Visit 1), Day 7±1 day	Phase I Cannabis Visit (Visit 2), Day 14±1 day	Phase I Cannabis + Exercise Visit (Visit 3), Day 21±1 day	Phase I Cannabis Visit (Visit 4), Day 28±1 day	Phase I Cannabis + Exercise Visit (Visit 5), Day 35±1 day	Phase II Cannabis Visit (Visit 6), Day 42±1 day	Phase II Cannabis + Exercise Visit (Visit 7), Day 49±1 day	Phase II Cannabis Visit (Visit 8), Day 56±1 day	Phase II Cannabis + Exercise Visit (Visit 9), Day 63±1 day
Informed Consent	X									
Eligibility Questionnaire	X									
Physical Activity Readiness Questionnaire	X									
Height	X									
Weight	X	X	X	X	X	X	X	X	X	X
Blood Pressure and Heart Rate	X	X	X	X	X	X	X	X	X	X
Urine Test	X	X	X	X	X	X	X	X	X	X
Inquiry of Changes to Health and Prescription Status		X	X	X	X	X	X	X	X	X
VO 2 Max Test	X									
Pulse Wave Velocity		X	X	X	X	X	X	X	X	X
Brachial Artery FMD		X	X	X	X	X	X	X	X	X
Echocardiography		X	X	X	X	X	X	X	X	X
20 Minute Maximal Cycling Exercise		X		X		X		X		X
Vaporization of High THC Cannabis			X	X				X	X	
Smoking of High THC Cannabis					X	X				
Vaporization of High CBD Cannabis							X			X
Indirect Calorimetry/CPET	X	X		X		X		X		X
Microneurography (MSNA)			X							
Stress Echocardiography			X		X		X		X	
Measurement of Continuous Blood Pressure		X	X	X	X	X	X	X	X	X
ECG	X	X	X	X	X	X	X	X	X	X
Impedance Cardiography		X		X		X		X		X
Drug Effects Questionnaire			X	X	X	X	X	X	X	X

*This study will use a randomized crossover design. Phase I of this study will occur prior to the initiation of phase II. If a participant enters the study in phase II, but did not participate in phase I, they will be required to complete the introductory and exercise control visits. Visits 2-5 and 6-9 will occur in a randomized order, which will be individualized for each participant.*

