### 3 OBJECTIVES AND ENDPOINTS

OBJECTIVES	ENDPOINTS	JUSTIFICATION FOR ENDPOINTS
Primary		

The primary objective of the current study is to determine the acute effects of cannabis consumption at rest and during exercise on the human cardiovascular system, with particular focus on the influence of method of consumption (smoking vs. vaporizing), and cannabinoid composition (THC vs. CBD).
	
The primary endpoints will be measures of arterial stiffness, endothelial function, muscle sympathetic nerve activity, and cardiac function.
 
Arterial stiffness and endothelial function will be assessed via carotid-femoral pulse wave velocity and brachial artery flow-mediated dilation.
 
Muscle sympathetic nerve activity (MSNA), or microneurography, will be characterized using indices of sympathetic outflow, such as burst incidence and burst frequency.
 
Cardiac function will be assessed using echocardiography. Primary endpoints will be measures of systolic function, diastolic function, and tissue mechanics. These measures include but are not limited to ejection fraction, E/A ratio, myocardial twist, and myocardial strain.
	
Carotid-femoral pulse wave velocity has been chosen as a primary endpoint as it has been shown that cigarette smoking, which is not dissimilar to cannabis smoking in many ways, results in arterial stiffening both acutely and chronically. Furthermore, the relationship between pulse wave velocity and risk of cardiovascular events has been well documented. Previous research has identified that a 1SD increase in pulse wave velocity is correlated with a 16-20% increase in risk for cardiovascular events.
 
Similar to pulse wave velocity, brachial artery flow-mediated dilation has been shown to have predictive value in determining risk of cardiovascular events in healthy subjects.
 
Microneurography (MSNA) will allow recording of the electrical activity of sympathetic nerves. This technique provides insight into the autonomic control of the cardiovascular system. This technique will further allow exploration of the mechanisms underlying other primary outcomes. Burst incidence and burst frequency are commonly reported measures of muscle sympathetic nerve activity.

OBJECTIVES	ENDPOINTS	JUSTIFICATION FOR ENDPOINTS

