## 4 STUDY DESIGN

### 4.1 OVERALL DESIGN

The study will use a randomized cross-over design. It will be structured by division into two phases. Both phases will examine the acute cardiovascular response to cannabis consumption,

both at rest and during exercise. *Phase I* will examine if and how this response differs whether cannabis is smoked or vaporized. *Phase II* will examine how this response is influenced by cannabinoid concentration within inhaled cannabis. Phase II of the current study will use a single-blind design, with participants being unaware of the relative cannabinoid concentrations of the cannabis they consume. Cannabis will be inhaled using methods of smoking (phase I only) or vaporization (phase I and II). Each experimental study visit (study visits 2-9), 100mg of cannabis will be consumed via one of the two aforementioned methods of inhalation, followed by a subsequent rest period, or by 20 minutes of exercise. Primary endpoints will be examined pre- and post-consumption each visit (with the exception of muscle sympathetic nerve activity, which will only be performed on a single study visit), while secondary endpoints will be recorded during exercise.

Each phase of the study will require participants to complete an introductory and control visit, as well as 4 experimental study visits, where cannabis inhaled under alternating conditions (phase I: smoking vs. vaporizing high THC cannabis, phase II: high CBD cannabis vs. high THC cannabis) followed by exercise, or a time-matched rest period. The order in which these visits will occur will be randomized, and individualized for each participant. A within-subjects design will be utilized, so that each participant completes each condition. High THC cannabis used will be the cannabis strain “Rex”, while the high CBD strain will be “Kalea”. The dose size and strength will not be altered throughout the course of the study.

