- Muscle sympathetic nerve activity will only be performed before and after vaporizing of high THC cannabis. Microneurography will be performed by inserting a tungsten microelectrode into the peroneal nerve. Upon identification of a sympathetic nerve

bundle, baseline activity will be recorded for a maximum of 10 minutes. Participants will then follow the standard smoking protocol, while sympathetic activity is recorded during the rest period.

- Cardiac function will be assessed using echocardiography. Echocardiography will be performed prior to exercise during the exercise control visit, and will be performed after consumption of cannabis on each study visit. Ejection fraction, E/A ratio, myocardial twist, and myocardial strain have all been chosen as these are standard measures for evaluating respective aspects of cardiac function. The heart will be viewed via the parasternal and apical imaging windows, and will be imaged using the Vivid-I ultrasound system.

Efficacy assessments of secondary objectives are as follows:

- Blood pressure, heart rate, and myocardial oxygen demand will be determined using a Finapres device which measures beat-to-beat heart rate and blood pressure using a finger cuff. The product of these two endpoints will represent the rate-pressure product, an indicator of myocardial oxygen demand. These outcomes will be assessed in the 20-minute period following cannabis consumption during each study visit. Therefore, recordings will take place at rest and during exercise depending on the given study visit.
- Indirect calorimetry will be performed during all exercise bouts, and will be used to evaluate oxygen consumption and other cardio-respiratory measures such as respiratory exchange ratio, minute ventilation, and caloric expenditure. Participants will be instrumented prior to each exercise bout, and measurement will only take place during the exercise bout.
- Participants will also be asked to provide ratings of perceived exertion every 2 minutes during each exercise bout. Ratings will be collected using the 6-20 Borg scale of perceived exertion.
- Exercise performance will be quantified by numerous endpoints such as average power output, and total work completed in the allotted exercise period (20 minutes). These outcomes will be assessed using the manufacturer software provided with the cycle ergometer that will be used in all exercise bouts.

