## 9.4 STATISTICAL ANALYSES

### 9.4.1 GENERAL APPROACH

Our study will be divided into two phases each of which will be analyzed independently. All tests of significance will be two-tailed, and statistical significance will be based upon an alpha error probability of 5% and a power for 80%. The data will be evaluated using both parametric and non-parametric tests, as applicable. If the data are found to be not normally distributed, the raw data will be transformed using an appropriate transformation model in order to perform the parametric assessments. Non-parametric tests will be performed on raw data. The data will be assessed as continuous and will be presented as means with standard deviations. A one-way analysis of covariance will be used to assess the treatment

effects (Phase I: exercise, vaporizing THC, smoking THC, vaporizing + exercise THC, smoking THC + Exercise, Phase II: exercise, vaporizing THC, vaporizing CBD, vaporizing + exercise THC, Vaporizing CBD + Exercise) on the primary endpoints. Covariates will be introduced into the models in order to assess the impact of certain potential factors on outcome, including fitness, blood pressure, resting heart rate, and any other factors that are observed during the study that appear to potentially influence the outcome.

Our secondary endpoints will be assessed using a repeated measures one-way ANOVA and paired t-tests. If there are significant interactions differences between pairs of means will be determined with a Bonferroni post-hoc test.

---

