#### 9.4.2 ANALYSIS OF THE PRIMARY EFFICACY ENDPOINT(S)

All primary endpoints will be measured as continuous variables and will be repeated after each intervention performed on a given study visit. A one-way ANCOVA will be used to assess treatment effects. Covariates will include basic cardiovascular and haemodynamic variables that may confound primary endpoints. These covariates include heart rate, blood pressure, and pulse wave velocity. Results will be presented as adjusted means with standard deviations. Primary endpoints will only be analyzed for participants who complete the entirety of at least one phase of the proposed study. Missing data will be imputed using mean imputation from all other measurements collected from the given participant. Outliers will be included and excluded in independent analysis, both of which will be reported.

---

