## 1. STATISTICAL CONSIDERATIONS

### 1. STATISTICAL HYPOTHESES

- Primary Efficacy Endpoint(s):
  1. Pulse Wave Velocity will be increased following exercise, smoking high THC cannabis, and vaporizing high THC cannabis relative to resting baseline; effects of cannabis consumption and exercise are likely to be additive. Vaporizing high CBD cannabis will not increase pulse wave velocity.
  2. Percent flow mediated dilation will be decreased following exercise and smoking high THC cannabis; effects are likely to be additive. Vaporizing both high THC and high CBD cannabis will not decrease percent flow mediated dilation.
  3. Ejection fraction will be decreased following smoking and vaporizing high THC cannabis. Exercise and vaporization of high CBD cannabis will not be associated with reductions in ejection fraction.
  4. E/A Ratio will be decreased following high THC cannabis smoking only.
  5. Myocardial strain will be decreased following high THC cannabis smoking and vaporizing only.
  6. Myocardial twist will be decreased following high THC cannabis smoking and vaporizing only.
  7. Burst Frequency will be increased following high THC cannabis only.
  8. Burst Incidence will be increased following high THC cannabis only.
- Secondary Efficacy Endpoint(s):
  1. Systolic Blood Pressure will be increased following cannabis consumption and will be decreased following all bouts of exercise.
  2. Diastolic blood pressure will be unchanged under all conditions
  3. Heart rate will be increased following cannabis consumption and exercise.
  4. Stroke volume will be increased with exercise, and will be reduced following cannabis consumptions. These competing effects will result in an attenuation of increases in stroke volume when exercise is preceded by cannabis consumption.
  5. Cardiac output will be unchanged under all conditions
  6. Work completed will be reduced when preceded by cannabis consumption of all forms
  7. Average power output will be reduced when preceded by cannabis consumption of all forms
  8. Oxygen consumption will be reduced when exercise is preceded by consumption of high THC cannabis
  9. Rating of Perceived Exertion will be increased following consumption of high THC cannabis
  10. Rate-pressure product will be increased during exercise, when the bout is preceded by cannabis consumption.

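### Hypotheses 7 and 8 say MSNA rises after high THC only, but MSNA is recorded only around vaporised THC at one visit, so the plan can estimate a pre-post change but cannot test exclusivity or run its five-condition ANCOVA

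*Protocol*

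**What the plan says.** Protocol section 3 makes MSNA primary: "The primary endpoints will be measures of arterial stiffness, endothelial function, muscle sympathetic nerve activity, and cardiac function". It is to be characterised by burst frequency and burst incidence, which are two indices taken from the same nerve recording.

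Protocol 9.1 and SAP 1 give eight primary hypotheses. The seventh is "Burst Frequency will be increased following high THC cannabis only" and the eighth is "Burst Incidence will be increased following high THC cannabis only".

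Three places describe when MSNA is recorded, and they agree:
- Protocol 8.1: "Muscle sympathetic nerve activity will only be performed before and after vaporizing of high THC cannabis". The same paragraph provides for a baseline of up to 10 minutes before inhalation.
- Protocol 4.1 requires primary endpoints before and after consumption at each visit, "with the exception of muscle sympathetic nerve activity, which will only be performed on a single study visit".
- The schedule in 1.3 has one mark in the microneurography row, under Visit 2 (Phase I, vaporised high THC, no cycling). The exercise control visit, the smoking visits, the cannabis-plus-exercise visits and all Phase II visits are unmarked.

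For the analysis, Protocol 9.4.2 says of the primary endpoints: "A one-way ANCOVA will be used to assess treatment effects". Protocol 9.4.1 lists the levels, for instance "Phase I: exercise, vaporizing THC, smoking THC, vaporizing + exercise THC, smoking THC + Exercise", with five more for Phase II. SAP 4.1 and 4.2 repeat this. Neither document makes an exception for MSNA or names another analysis for it. Paired t-tests appear only for the secondary endpoints.

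**The concern.** A claim that MSNA rises after high THC and after nothing else needs MSNA data from something else. A one-way ANCOVA across five conditions needs the endpoint in at least two of them. Neither requirement is met.

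Two things are at stake. First, a significant pre-post rise could be reported as confirming a prespecified THC-specific effect. The design cannot separate such a rise from the passage of time or from the inhalation manoeuvre itself, which includes a 10-second breath hold (Protocol 6.1.2). Second, a primary endpoint would in practice be analysed by a method chosen after the data are in, because the prespecified one cannot be fitted.

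**Working it through.** **1. The plan's own figure.** The only design number nearby is the 15 participants in Protocol 9.2, based on flow-mediated dilation, pulse wave velocity and longitudinal strain. MSNA is not among the inputs. For a paired t-test, the SD of the difference is √(s₁² + s₂² − 2·r·s₁·s₂). The pre-post correlation r is not given. For strain with r = 0.5 assumed:
- SD = √(1.2² + 1.9² − 2 × 0.5 × 1.2 × 1.9) = √2.77 = 1.664
- standardised change = 1.3 / 1.664 = 0.781
- n = 15, with power 0.803 (two-sided alpha 0.05)

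At r = 0, 0.3 and 0.7 the strain requirement is 26, 20 and 11. At r = 0.5 dilation after exercise needs 11 and pulse wave velocity 9, so strain drives the figure. The stated 15 is thus reproducible under an assumed correlation of 0.5. Nothing below depends on it.

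**2. MSNA data against the ANCOVA levels, Phase I.**

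| Condition in 9.4.1 | MSNA recorded? |
|---|---|
| Exercise | No |
| Vaporised THC, rest | Yes, before and after |
| Smoked THC, rest | No |
| Vaporised THC + exercise | No |
| Smoked THC + exercise | No |

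Planned treatment degrees of freedom: 5 − 1 = 4. Available for MSNA: 1 − 1 = 0. Of the 5 × 4 / 2 = 10 pairwise comparisons, none can be estimated.

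**3. Phase II.** Vaporised THC at rest is also one of the five Phase II levels, but the schedule marks no MSNA at any Phase II visit. The two phases are to be analysed independently. Even if the Phase I recording were carried across, it would fill one level, and the degrees of freedom would still be 0. No MSNA is planned with CBD under any reading.

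**4. What each part of hypotheses 7 and 8 needs.**
- Rise after vaporised high THC: needs before and after values at that visit. Available.
- Rise after smoked high THC, which the wording also covers: needs a smoking-visit recording. Not available.
- No rise after CBD or exercise: needs those recordings. Not available.

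**5. The imputation rule.** Protocol 9.4.2 and SAP 4.2 replace missing values with the mean of the participant's other measurements, and do not say whether unrecorded conditions count as missing. Suppose they did, and that the mean were taken over that participant's MSNA values: b before and a after. Each of the other four Phase I conditions would receive (a + b)/2. The contrast of vaporised THC with each would be a − (a + b)/2 = (a − b)/2, half the pre-post change. It would appear identically against all four, and so resemble an exclusive effect that was never observed.

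**6. What the design does support.** A paired pre-post comparison with 15 participants has 80% power (two-sided alpha 0.05) for a standardised change of about 0.78. The documents give no mean or SD for MSNA, so the power for hypotheses 7 and 8 cannot be stated.

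**The case against.** The restriction is disclosed. Protocol 4.1 excepts MSNA from the every-visit rule and 8.1 repeats the limit. Section 3 also gives MSNA a partly mechanistic role, and a reader could take a paired pre-post comparison as obviously intended. That is a fair account of the likely intent, but it does not reach the analysis sections. Those name ANCOVA alone for primary endpoints and say that every primary endpoint is measured again following each intervention, which contradicts 4.1. The general allowance in 9.4.1 for parametric or non-parametric tests as applicable does not name a paired test for a primary endpoint.

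The word *only* might describe scope: high THC is the only condition in which MSNA is studied. This is possible but less likely. Hypotheses 4 to 6, directly above, use the word for exclusivity across conditions. The ANCOVA mismatch stands on either reading.

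A reader might also infer more than the documents support:
- That there is no cannabis-free MSNA recording and so nothing to compare. Protocol 8.1 provides a baseline before inhalation. What is absent is a time-matched or non-THC control.
- That two of eight primary hypotheses are wholly unanswerable. Their directional part can be tested for the vaporised route, and the two indices come from one recording, so this is one measurement problem.
- That the recorded condition lies outside Phase II. Vaporised THC at rest is on the Phase II list. The supportable statement is that no Phase II visit is marked for MSNA.

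**Conclusion.** The point holds in this form. The exclusivity part of hypotheses 7 and 8, and any smoked-THC part, has no data behind it. The ANCOVA assigned to all primary endpoints has no treatment contrast for MSNA: one of five Phase I conditions recorded, 0 degrees of freedom against 4. A change from before to after vaporised high THC can be estimated, without a concurrent control.

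This touches two of the eight primary hypotheses, through one recording, and leaves the other six unaffected. The ANCOVA part rests only on the recording schedule, on which 1.3, 4.1 and 8.1 agree. The exclusivity part also rests on reading *only* as hypotheses 4 to 6 use it. The imputation hazard is conditional: the plan does not say that unrecorded conditions would be imputed, but it does not exclude it. The plan should be corrected before analysis.

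**What to change.** - **Protocol 9.1 and SAP 1:** restate hypotheses 7 and 8 as an increase in burst frequency and in burst incidence from before to after vaporised high-THC cannabis, and delete *only*.
- **Protocol 9.4.1 and 9.4.2, SAP 4.1 and 4.2:** exempt MSNA from the five-condition ANCOVA and from the sentence that has all primary endpoints re-measured following each intervention. Section 9.4.1 must be included because the list of conditions sits there.
- **Same analysis sections:** name a paired pre-post test with a 95% confidence interval for MSNA, and state that conditions in which MSNA was not scheduled are not missing data and are not imputed.
- **Same analysis sections:** state that no THC-specific or method-specific claim will be made from MSNA.
- **Protocol 8.1:** the MSNA paragraph describes a vaporising visit and then refers to the smoking protocol. The two statements should be reconciled.

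The cost is wording in two documents and a narrower MSNA claim, with no added visits or procedures. If the sponsor wants to keep the exclusivity claim, MSNA would have to be recorded in comparator conditions, at the price of further microneurography sessions. Making MSNA a secondary or mechanistic endpoint is another option, but it would still need the named paired analysis.
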